## Study Design and Outcomes Overview

This is a single arm pilot and feasibility study to adapt the Shed-MEDS intervention to the memory care setting. The Shed-MEDS intervention is a multistep deprescribing protocol which considers patient and disease factors, life expectancy, goals of care, and appropriate treatment targets. Medication-specific factors such as drug-drug interactions, drug-disease interactions, and drug-specific safety profiles are also incorporated. Finally, patient preferences and primary prescriber input are key to final deprescribing actions by identifying the medications patients are willing to deprescribe and seeking their primary prescriber's agreement. In this intervention, deprescribing is defined as either stopping a medication or reducing the dose/frequency of a medication.

The primary study setting is two assisted living facilities (ALFs) with dedicated memory care units.

Eligible residents are ALF residents aged 65 years or older with a dementia diagnosis and experiencing polypharmacy as defined by 5 or more medications.

Primary Outcome is the number of medications deprescribed, either stopped or reduced dose, 90-days after intervention completion.

Secondary Outcome is the impact of deprescribing on behavioral symptoms of dementia and resident quality of life.

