Our research team recently completed a patient-centered deprescribing intervention (Shed-MEDS) that targeted older hospitalized adults that required ongoing post-acute care (PAC). The nurse-practitioner or pharmacist-led deprescribing intervention resulted in statistically significant reductions in total medications and the combined burden of anticholinergic and sedative medications as measured by the drug burden index. Reductions were achieved at the end of the intervention (at the time of PAC discharge), and up to 90 days following the end of the intervention. Despite these successes, we do not know the feasibility or effect-size of a similar intervention implemented in a memory care ALF for PWD and their proxies. Thus, we aim to perform a single-arm, repeated-measures within-subjects feasibility pilot of the Shed-MEDS deprescribing intervention among PWD experiencing polypharmacy and their caregivers at the Abe's Garden dementia care ALF. **Our overarching hypothesis is that implementing the Shed-MEDS deprescribing protocol within a dementia care ALF will be feasible and reduce medications without worsening the quality of life for PWD.**

**Specific Aim 1:** Determine the feasibility of implementing the Shed-MEDS deprescribing intervention among PWD residing in a dementia care ALF.

- Aim 1a. Family proxy acceptability will be measured via the revised Patient Attitudes Toward Deprescribing (rPATD) designed for surrogates and through documentation of barriers and enablers to deprescribing recommendations shared via proxy interviews.
- Aim 1b. Implementation of the Shed-MEDS intervention will be assessed by the proportion of deprescribing recommendations acceptable to primary prescribers and family proxies of PWD.

**Specific Aim 2:** Document the effects of the Shed-MEDS deprescribing intervention on medication burden among PWD.

- Aim 2a: Compared to a pre-intervention period, the Shed-Meds intervention will result in significant increases in the total number of medications deprescribed, as defined by terminations at the end of 90 days.

- Aim2b: Compared to a pre-intervention period, the Shed-Meds intervention will result in a significant decrease in the anticholinergic and sedative drug burden of prescribed medications at the end of 90 days.

**Specific Aim 3:** Document the effects of the patient-centered deprescribing intervention (Shed-MEDS) on the quality of life of PWD.

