### Schedule of Assessments

**Table 1. Data Collection Schedule**

Measures	3-month Retrospective Review ∞	Enrollment	30- & 60-day Follow-up	90-day Follow-up
Demographics and Health Status				
Age, Gender, Race/Ethnicity, Education Level*		X		
Comorbidities*		X		
Cognitive Impairment (BIMS)	X*	X		X
Status: Long-Term Care, Hospice, Death*	X	X		X
Medications				
Total number of medications*	X	X	X	X
Sedative & Anticholinergic Drug Burden Index	X	X	X	X
Quality of Life				
DEMQoL-Proxy		X		X
BPSD*	X	X	X	X
Safety				
Falls*	X	X	X	X
Emergency Room Visits & Hospitalizations*	X	X	X	X
Feasibility				
RPATD (surrogate)		X		
Surrogate agreement w/ deprescribing recommendations		X	X	
Provider agreement w/ deprescribing recommendations		X	X	
Total number of conversations w/ prescribing MD/NPs		X	X	X
Total number of conversations with surrogates		X	X	X

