### **Primary Outcomes - Medications**

Total number of Medications: The primary data source is the resident's ALF medication administration record (MAR). We include both prescription and over-the-counter medications (OTC) (vitamins, herbal supplements also included) administered by the following routes: oral, intravenous, intramuscular and ophthalmologic medications. All surrogates receive a baseline structured interview with specific prompts for OTC medications they may be providing directly (and not administered by the facility).

PIMs are defined by previously published lists including the recently updated Beers criteria, the STOPP criteria, as well as the RASP list, for which there is a large degree of overlap. The total number of PIMs is the sum of medications that are found on any of these explicit lists.

Drug Burden Index (DBI): A DBI score is calculated separately for anticholinergic (DBIAC) and sedative medications (DBIs), which have been strongly linked to functional impairment, falls, and delirium. The drug burden is the sum of each individual anticholinergic/sedative medication's prescribed daily dose divided by the sum of the minimum effective dose (as estimated by the FDA minimum recommended dose) and the patient's daily dose. The DBI includes over-the-counter medications. We will calculate the DBI at baseline and all follow-up timepoints. Importantly, the DBI captures reductions in dose, even when total number of medications is not reduced.

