### Pre-Review (Target Medications for Deprescribing)

Using medical record data only, a study NP will gather the following information for each medication: (1) Medication – Indication pairing: For each medication, an indication (i.e., diagnosis or symptom) will be identified. If an indication does not exist, “no indication indicated” will be specified; and, (2) De-prescribing rationale: Each medication will be assessed for the potential rationales for deprescribing shown in Table 2, indicating all applicable rationales.

All medications, both prescription and OTC including vitamins and herbal supplements, are reviewed for potential deprescribing. Select medication classes will not be under consideration for active deprescribing, which include the following:

- Anti-rejection medications for organ/ bone-marrow transplantation
- Chemotherapeutic medications for the treatment of known solid organ or hematologic malignancy.

The above medications may be deprescribed during the study period; however, it would solely be under the direction of the primary prescriber of the medication.

Deprescribing Priority: Although any rationale may be appropriate for deprescribing medications, a study NP will establish a priority level of 1 (low) to 10 (high) for discussing deprescribing recommendations. Priority will consider potential harm of the medication and potential effects on geriatric syndromes. It may be inappropriate to deprescribe multiple medications simultaneously; thus, prioritization may guide the surrogate interview and the deprescribing order.

**Deprescribing Action Recommendations:** For any medications recommended for deprescribing, the study NP will recommend a deprescribing action: (1) Stop now without need for monitoring; (2) Stop with symptoms/physiologic monitoring; (3) Stop at specified time point; (4) Reduce over time with monitoring until medication is stopped; (5) Reduce to lower dose without need for monitoring; (6) Reduce to lower dose with symptoms /physiologic monitoring. All recommendations will be discussed with primary prescribers (**Step 2b**) and surrogate decision-makers (**2c**).

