## STATISTICAL CONSIDERATIONS

### Sample Size & Attrition

Abe's Garden administration reported that all current residents lack decision-making capacity for healthcare decisions, and that all have surrogate decision makers. We estimate that the majority of the 41 residents/surrogates will participate in the study and conservatively estimate, based on investigators' work in previous studies in long term care, that attrition will be approximately 10-15%. We anticipate that some residents may die during the study and some surrogates may decline participation.

Power consideration: Given this is a pilot study, no formal power analysis will be conducted. But this pilot data would serve as a further guide for the power analysis for the following multi-center trial in preparation to test the clinical effectiveness of deprescribing among PWD in ALF care settings.

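### The declared primary outcome counts medications stopped or reduced, Aim 2a counts terminations only, and no planned analysis covers the declared count

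*Combined protocol and SAP*

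**What the plan says.** The combined protocol and SAP describes the medication outcome in several places.

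- **Study Design and Outcomes Overview.** "Primary Outcome is the number of medications deprescribed, either stopped or reduced dose, 90-days after intervention completion". The same section says that "deprescribing is defined as either stopping a medication or reducing the dose/frequency of a medication". The definition includes frequency; the outcome sentence mentions dose only.
- **Overview and Objectives, Aim 2a.** Compared with a pre-intervention period, the intervention is expected to produce "significant increases in the total number of medications deprescribed, as defined by terminations at the end of 90 days". Aim 2b concerns anticholinergic and sedative drug burden.
- **Table 1.** The Medications block schedules "Total number of medications" and the DBI.
- **Primary Outcomes – Medications.** This section defines total number of medications, potentially inappropriate medications (PIMs) and the DBI. It notes that "the DBI captures reductions in dose, even when total number of medications is not reduced".
- **Statistical Considerations, Outcomes.** A GEE model is planned for the medication outcomes of Aim 2, with no variable named.
- **Data Analyses, Repeated measures.** Total number of medications is named among the main outcomes, assessed at enrollment, 30, 60 and 90 days.

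**The concern.** Two current sections give different counting rules for one quantity, and that quantity is the declared primary outcome. A drug still taken at a lower dose at day 90 is a success under the overview and contributes nothing under Aim 2a. The sections that should settle the matter (Table 1, the outcome definitions and the analysis text) introduce a third quantity, the net number of drugs on the list, and never mention the stopped-or-reduced count.

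Two things are at stake. First, the primary result depends on which section the analyst follows, and as written that choice could be made after the data are seen. Second, the Sample Size & Attrition section says "this pilot data would serve as a further guide for the power analysis for the following multi-center trial", and the Limitations paragraph says the design was chosen to estimate effect sizes for later trials. An effect size is only usable if the variable behind it is fixed.

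**Working it through.** The plan gives no power calculation, effect size or standard deviation for this outcome, so there is no figure to reproduce. The check has three parts.

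**1. Do the rules score the planned actions differently?** The Pre-Review section lists six recommended actions.

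| Action | Overview count | Aim 2a count |
|---|---|---|
| 1–3: stop (three variants), once carried out | yes | yes |
| "4) Reduce over time with monitoring until medication is stopped", taper finished by day 90 | yes | yes |
| Same action, taper unfinished at day 90 | yes | no |
| "5) Reduce to lower dose without need for monitoring" | yes | no |
| 6: lower dose with monitoring | yes | no |

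Actions 5 and 6 always differ, and action 4 can. The documents do not say how often each will be used.

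**2. Does any planned analysis cover the declared count?** The GEE paragraph can be read in two ways.

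- Through the aims, it covers terminations (2a) and DBI (2b).
- Through the Medications block of Table 1, it covers total number and DBI.

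Neither includes the number stopped or reduced. DBI records dose reductions only for anticholinergic and sedative drugs. The surrogate and provider counts under Secondary Outcomes record agreement to deprescribe, and Table 1 schedules them at enrollment and the 30- and 60-day follow-up. They cannot stand in for a count achieved at 90 days.

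**3. How far apart can the quantities be?** For one resident let s = stopped, r = reduced only, a = newly started. Then:

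- overview count = s + r
- Aim 2a count = s
- change in total number = a − s

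Illustrative residents (s, r and a are assumed; the documents give no such rates):

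| s | r | a | Overview | Aim 2a | Change in total |
|---|---|---|---|---|---|
| 2 | 0 | 0 | 2 | 2 | −2 |
| 0 | 2 | 0 | 2 | 0 | 0 |
| 1 | 1 | 1 | 2 | 1 | 0 |
| 2 | 1 | 2 | 3 | 2 | 0 |

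With f = r/(s + r), the Aim 2a count divided by the overview count is s/(s + r) = 1 − f. That gives 0.90, 0.80, 0.70 and 0.60 at assumed f of 0.1, 0.2, 0.3 and 0.4.

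For the comparison with the pre-intervention period, the two within-resident differences are (s + r)post − (s + r)pre and s(post) − s(pre). They differ by r(post) − r(pre), which the documents do not allow us to estimate.

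**The case against.** The best defence is that the plan does define what it analyses. The GEE paragraph points to Aim 2, and Aim 2a carries an operational definition, so terminations enter by reference. The list in the Repeated measures paragraph is also not exhaustive. This stands in part: a reader might infer that Aim 2a has no analysis at all, and the text does not support that. But the count brought in this way is still not the declared primary outcome.

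A second defence is a deliberate division of labour, with counts for stops and DBI for dose. The plural heading Primary Outcomes – Medications fits that. The division is incomplete, because dose reductions in drugs that are neither anticholinergic nor sedative are left out. The heading does, however, argue against demoting total number, PIMs or DBI, and the inconsistency can be repaired without doing so.

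Third, a reader might take the risk section's preference for titration over full withdrawal as proof that many drugs will remain at a lower dose at day 90. That wording may mean gradual rather than abrupt stopping; the Potential Benefits section speaks of tapers, and action 4 ends in a stop. The argument rests on actions 5 and 6 and does not need it.

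Finally, this is a single-arm pilot without a power analysis, whose main aims are described as feasibility. That limits the consequences, but the plan still declares a primary outcome and two-sided tests at 0.05.

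**Conclusion.** The inconsistency is real and should be resolved before analysis. The declared primary outcome and the only hypothesis about it use different counting rules, and the plan followed as written analyses something other than the declared outcome. This is established from the text alone.

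The size of the discrepancy is not known. The terminations count is (1 − f) of the stopped-or-reduced count, and any value of f is an assumption. No sample size, power or alpha figure in this pilot changes.

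It is tempting to go further and say that the next trial would need 1/(1 − f) times as many participants. The documents do not support any such multiplier: that trial's design and primary outcome are not given, and the Sample Size section speaks only of pilot data as a guide. The result also turns on f being equal in both arms. Take n proportional to (1/m0 + 1/m1)/(log(m1/m0))², with assumed stopped-or-reduced means of 1 (control) and 2 (intervention), giving 1.5/0.480 = 3.12.

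- With f = 0.4 in control and 0.1 in intervention, the means become 0.6 and 1.8: 2.222/1.207 = 1.84, or 0.59 times as many.
- With these reversed, the means become 0.9 and 1.2: 1.944/0.0828 = 23.5, or about 7.5 times as many.

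Even the direction is undetermined.

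**What to change.** Before analysis, reconcile Aim 2a and the overview on one primary count, using the overview's own definition: the number of medications on the enrollment list that are stopped, or at a lower dose or frequency, 90 days after intervention completion. Add frequency to the outcome sentence and replace the terminations wording in Aim 2a. Name the count in Table 1, Primary Outcomes – Medications, the Outcomes analysis paragraph and the Repeated measures paragraph. Report the terminations-only count beside it.

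Apply the same rule to the 3-month retrospective period, relative to the list at its start. No study recommendations exist in that period, so all changes should count whoever initiated them. Compare the two period counts within resident: a change count is not defined at enrollment, so it does not fit the four-time-point model. Measured from enrollment, the follow-up window also includes the intervention itself and may be longer than the look-back; report both lengths.

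Keep total number, PIMs and DBI as additional medication outcomes. If data have already been examined, report both counts and say so.

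The cost is text edits, plus abstraction of dose and frequency from facility records for all drugs where this is not already done. No new visits or participants are needed.

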## BACKGROUND AND SIGNIFICANCE

Polypharmacy, most commonly defined as the concurrent use of five or more prescription and over the counter (OTC) medications, affects 40%–50% of older adults in the United States and is associated with geriatric syndromes, decreased medication adherence, increased adverse drug events, and increased health care utilization and costs. Deprescribing, the systematic process of medication cessation, has been identified as an effective way to mitigate polypharmacy and inappropriate medication use. Furthermore, patients' attitudes toward their medications and willingness to deprescribe often vary by medication. To understand medication-specific barriers and enablers, clinicians need to engage patients in deprescribing conversations to ensure that their preferences, goals of care, and concerns are known. Recent studies suggest that the majority of adults aged 65 and older express a willingness to deprescribe a medication if their clinicians agree, and that they wish to be involved in the decision-making process.

Although people with dementia (PWD) are more likely to have polypharmacy and to take unnecessary medications, few studies have assessed attitudes toward deprescribing in this population. A recent study on deprescribing attitudes in PWD showed that the majority of participants were agreeable to stopping a medication if advised by their physician. Proxy respondents in this study were less agreeable to deprescribing, echoing previous findings that have shown caregiver resistance to deprescribing of antipsychotics due to concern about the management of behavioral and psychological symptoms of dementia (BPSD). Further, deprescribing interventions for PWD have been focused on particular medication classes and have been conducted in the hospital and skilled nursing facility (SNF) settings. To date, we have found no published deprescribing studies of PWD residing in an assisted living facility (ALF).

This proposed pilot study will enable investigators to expand upon knowledge gained during the Shed-MEDS randomized clinical trial and allow examination of this deprescribing intervention in the ALF setting, something that has never been done before. There are an estimated 29,000 assisted-living facilities (ALFs) nationwide serving approximately one million older adults. ALFs are group residential care facilities not licensed as nursing homes, although 34% of ALF residents have a diagnosis of Alzheimer's Disease or a related dementia and need assistance with daily care. A recent nationwide survey of 30,000 ALFs revealed dementia as one of the most prevalent chronic conditions, with nearly two thirds of all residents requiring caregiver assistance with 3 or more ADLs. The average length of stay in an ALF is 28 months, and most residents (59%) will eventually transition to a nursing home for care. Given these demographics, we believe an ALF may be an ideal setting for deprescribing interventions for PWD.

[figure not shown]
Shed-MEDS clinical trial was a patient-centered hospital-based deprescribing trial. Although the Shed-MEDS intervention showed medication reduction in hospitalized older adults discharging to a post-acute care facilities, its feasibility of use for older adults in other clinical settings is unknown. Participants in the Shed-MEDS clinical trial had many similarities to residents living at Abe's Garden, a licensed ALF in Nashville, TN that provides memory care for all residents: 21% had Brief Intervention for Mental Status (BIMS) 30 scores suggestive of dementia, 13% were living in an ALF setting prior to hospitalization, and 15.6% of participants were residing in an ALF at the time of study completion. The Shed-MEDS trial was unique in that it also measured deprescribing attitudes of surrogate decision makers of patients who were unable to consent.

Although PATD scores obtained during the study showed surrogates to be more hesitant about deprescribing, surrogates agreed to a higher percentage of deprescribing recommendations (64% v. 50%) than participants making their own medical decisions (64% to 50%) during the study's patient-clinician interviews. This suggests that surrogates who have an opportunity to engage with providers and receive medication education may be more amenable to deprescribing. Further, 23% of Shed-MEDS participants who did not finish the study dropped because of Hospice admission (exclusion criteria). This proposed pilot study includes Hospice beneficiaries, thus allowing investigators to examine the value of deprescribing in this population and to understand surrogate's deprescribing attitudes in PWD that receive subsequent hospice care.

# STUDY DESIGN

## Overview of Design

**Figure 1. Schematic of Study Design**

## Study Setting

The study was initially implemented at a single ALF; however, due to low enrollment, a second ALF was added six months into recruitment.

Abe's Garden is an ALF in Nashville, TN that provides long-term memory care for up to 42 PWD. At the time of the project inception, there are 41 residents, 12 of whom are Hospice beneficiaries. The average age of residents is 81 years, and their average length of stay is 1.6 years. Residents take an average of 7.78 medications, with 13 residents taking nine or more medications. On-site medical care is provided by a gerontological nurse practitioner and geriatrician, both of whom are employed by Vanderbilt University Medical Center (VUMC).

NHC Place at the Trace is a continuing care community in Nashville, TN, which includes Way Point ALF/ Memory Care. This memory care unit provides care for up to 32 residents, all of whom have dementia, and at time of the project there were 27 residents. Medical care is provided both in the outpatient setting, and by a gerontological nurse practitioner and geriatrician.

